25. Montreal Cognitive Assessment (MOCA) – in order to test participant for cognitive impairments [~10 minutes].
26. The Short Blessed Test, a six-item test, used as a diagnostic tool to differentiate patients with cognitive impairments from normal population will be administered. Subjects are asked to answer the items year and month, time of day, count backward 20-1, recite months backwards, and the memory phrase. This test will be administered in addition to the MMSE which also tests for cognitive impairment because the Short Blessed is known to be more sensitive to differences in levels of education and is also quicker to administer. (~ 3-4 minutes)

Pre and post intervention questionnaire – a series of questions to get a sense of the patient’s expectations, and general tiredness and motivation levels at the beginning and end of the study, and at the start of intervention each day. The questionnaire administered at the beginning of the study will ask questions regarding any allergies the patient may have and his/her experience with playing computer/video games. The post-intervention questionnaire is to get the patient’s feedback regarding their experience in the study.

B) Functional MRI scans

Participants will undergo an MRI scan without contrast lasting approximately 30 - 45 minutes at each of the five study timepoints. Participants’ pulse and respiratory rates will also be recorded in the scanner. This will require a pulse monitor (a device comfortably secured to a fingertip that uses light waves to measure pulse and blood oxygen levels) and a respiratory monitor (a belt comfortably secured around the torso that measures the depth and frequency of breaths). Neither monitor confers any risk to participants. fMRI scans will be collected while the participant is performing executed and imagined motor tasks in the scanner to examine corresponding brain activation.

Based on our ongoing study (approved under 2010-0004, 2015-0469), it is our experience that some of these patients will show contraindications for MRI (e.g., have implant or are claustrophobic etc.). We therefore propose to recruit patients who have contraindications for MRI and have them complete the behavioral assessments and intervention components of the study only.

C) Intervention

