All researchers and research staff involved in the study have completed Human Subjects and HIPAA training and will be continuously involved in data and safety monitoring. Data and safety monitoring will occur on a continuous basis. fMRI and EEG data will be reviewed by the PI, Co-I and a group of study team members on a continuous basis. All behavioral measures (e.g., ARAT, 9 holepegboard task, SIS etc.) will be reviewed by the study team within a week or two of collection.

Data Processing/Data Analysis

For Specific Aim 1:

1a) To investigate the efficacy of active FES vs. passive FES, as measured by changes in behavioral measures. A linear mixed model analysis in SPSS 22.0 will be run for each dependent measure (e.g., ARAT, SISand function) with Group (active, passive) as the between-participant factor and Time (baseline, mid, post, 1 month post) as the within-participant factor. The two baseline assessments will be averaged so as to get a stable measure of baseline performance prior to receiving intervention.

1b) To investigate the impact of BCI synchronized to FES on behavioral outcomes in the patients in the Active FES group: A post hoc analysis will be done to evaluate whether high-performers of the BCI classification task show more improvement in behavioral measures than low-performers of the BCI classification task. This will allow us to assess to what extent BCI synchronization to FES leads to improved stroke recovery. A median split of high to low performers on the BCI task will be done. We will then compare change in outcome measures of those with high performance on the BCI task (which is synchronized to FES) vs. those with low performance on the BCI task (when there is less synchronization between the BCI and FES) using unpaired t-tests. If there is a difference in the two groups then this is evidence that BCI synchronized to FES contributes to recovery, if there is no difference then this is evidence that BCI irrespective of synchronization to FES contributes to recovery.

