For Specific Aim 2: To track fMRI and EEG-BCI based brain reorganization changes and behavioral changes induced by active vs. passive FES. Changes in fMRI and EEG derived LI values over time will be compared in the 2 groups. Group differences in LI at each time-point will be evaluated using Mann-Whitney U test. To determine if there are significant main effects for groups and time, and significant interaction of Group X Time, we will perform Linear Mixed Model analyses. To test if change in fMRI and EEG derived LI, across multiple time-points correlate with change in behavioral measures: The difference in each measure, example from time-point 1(T1) to T2 (i.e. change score, Δ LI) will be calculated and separate correlation (Pearson or Spearman rho) analyses will be performed to see if change in fMRI and EEG significantly correlate with change in behavioral scores (Δ ARAT or Δ SIS-hand function etc).

EEG Data Statistical Analysis: The independent variables are the signed r-squared values and the coherence estimates. At individual participant level the data consists of average estimates per session for condition/movement/screening phase combination sets, and at group level the estimates consist of grand averages over sessions of each individual participant data in the group. Nonparametric statistical tests will be run by calculating Monte-Carlo estimates of the significance probabilities and critical values from the permutation distribution (Oostenveld et al., 2007), followed by correction for multiple comparison using false discovery rate (FDR). Our priori hypotheses regarding expected changes in the r-squared values and coherence as a result of intervention at C3 and C4 sites will be tested using paired t-tests in MATLAB.

For Specific Aim 3: To track DTI based brain reorganization changes and behavioral changes induced by active vs. passive FES. The Pearson r or non-parametric Spearman rank correlation test, as appropriate, will

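### Aim 2 tests LI between arms by unadjusted Mann-Whitney tests at each time point beside a Group x Time mixed model, with no deciding analysis and no multiplicity rule for LI

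*Combined protocol and SAP*

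**What the plan says.** All of this is in the combined protocol and SAP.

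- **Target.** Under Data Processing/Data Analysis, the Specific Aim 2 paragraph opens with "Changes in fMRI and EEG derived LI values over time will be compared in the 2 groups".
- **First analysis.** The next sentence reads "Group differences in LI at each time-point will be evaluated using Mann-Whitney U test". It gives no covariate and no baseline term.
- **Second analysis.** The sentence after that covers main effects of group and time, and for a "significant interaction of Group X Time, we will perform Linear Mixed Model analyses". Time levels, covariates and covariance structure are not given for LI.
- **Visits.** The Functional MRI scans section places a scan "at each of the five study timepoints". The number of visits at which EEG LI is derived is not stated.
- **Baseline handling.** Aim 1 specifies "Time (baseline, mid, post, 1 month post) as the within-participant factor" and adds that "The two baseline assessments will be averaged so as to get a stable measure of baseline performance prior to receiving intervention". Aim 2 contains neither statement.
- **Multiplicity.** The EEG paragraph that follows has permutation tests "followed by correction for multiple comparison using false discovery rate (FDR"). Its named variables are signed r-squared and coherence. LI is not among them.

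No primary LI visit or primary LI modality is named, and neither LI analysis is labelled exploratory or supportive.

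**The concern.** The aim is about change, but a Mann-Whitney test at a single visit compares levels. At the baseline visits, which each time point would include, patients have been randomized and not yet treated, so the test can find only chance imbalance. At later visits it sets aside the baseline LI already collected, which costs precision.

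The larger difficulty is the lack of a hierarchy. If one visit in one modality gives p < 0.05 while Group x Time does not, or the reverse, the plan does not say which answers Aim 2. With two modalities and several visits, such a split can easily arise by chance. At stake is how far the trial's between-arm LI result can be interpreted. The primary efficacy conclusion on ARAT is not affected.

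**Working it through.** **Inputs.**
- 72 patients per arm (Randomization).
- Two modalities (Aim 2). Five MRI visits (Functional MRI scans): two baselines, mid, post and 1 month, taking the visit structure from Aim 1.
- Assumed, because the documents do not give them: two-sided alpha 0.05 per test; EEG LI at the same five visits; independent modalities; equal within-patient correlation rho between visits of 0.5 to 0.9; a true difference of 0.4 SD at one visit.

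**1. The plan's own figure.** There is none for LI. The only sample-size calculation is for ARAT. Its 44 per cell reproduces as a paired t-test on pre-post change (6/12 = 0.5, two-sided 0.05, 90% power: n = 43.995) and has no bearing on LI.

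**2. Chance of at least one false-positive Mann-Whitney result.** For k independent tests the formula is 1 - 0.95^k:
- k = 6 (2 modalities x 3 post-baseline visits): 1 - 0.7351 = 26.5%
- k = 8 (2 x 4, baselines averaged): 1 - 0.6634 = 33.7%
- k = 10 (2 x 5): 1 - 0.5987 = 40.1%

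Repeated measures on the same patients are correlated, so these are ceilings. Simulating the tests themselves (normal data, 72 per arm, no effect, 20,000 trials per row; shorter runs move the results by about a point) gives:

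| rho | 3 post-baseline visits, 2 modalities | 5 visits, 2 modalities | 5 visits, 1 modality |
|---|---|---|---|
| 0.5 | 23% | 33% | 18% |
| 0.7 | 21% | 28% | 15% |
| 0.9 | 16% | 19% | 10% |

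The mixed-model tests come on top.

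**3. Power at one visit.** Power = Φ(0.4 / (SD x √(2/n)) - 1.96), with √(2/72) = 0.1667.
- Mann-Whitney: SD = 1 and effective n = 72 x 3/π = 68.75. 0.4/0.1706 = 2.345, so power is 65%.
- Baseline-to-post change, single baseline: SD = √(2(1 - rho)). At rho 0.5, SD = 1, 2.400, 67%. At rho 0.7, SD = 0.775, 3.098, 87%.
- Baseline-adjusted, single baseline: SD = √(1 - rho²). At rho 0.5, SD = 0.866, 2.771, 79%. At rho 0.7, SD = 0.714, 3.361, 92%.

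Adjustment therefore gains about 14 and 27 points over Mann-Whitney, but only about 12 and 5 over the change contrast.

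If both methods use the average of two baselines, the change variance is 1 + (1 + rho)/2 - 2 rho, which is 0.75 and 0.45 (power 79% and 95%). The adjusted variance is 1 - 2 rho²/(1 + rho), which is 0.667 and 0.424 (84% and 96%). The gap narrows further.

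MRI is optional, so fMRI LI will have fewer than 72 per arm. The number is not stated. As an illustration, 50 per arm gives 50% by Mann-Whitney, 52% and 73% by single-baseline change, and 64% and 80% by single-baseline adjustment.

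**4. Chance baseline imbalance.** Suppose baseline LI happens to differ by 0.33 SD (2 x 0.1667, about two standard errors) and there is no effect. A later Mann-Whitney test is then significant about 13% of the time at rho 0.5 and 20% at rho 0.7. With no imbalance the rates are 2.6% and 0.7%. Over all randomizations the rate remains 5%.

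**The case against.** The best defence is that the plan already contains the right kind of analysis. A Group x Time term uses baseline LI if baseline is a Time level, as it is in Aim 1, and the Mann-Whitney tests can be taken as descriptive support. The first half stands in part: a reader might infer that Aim 2 as a whole disregards baseline LI, and the documents do not support that. It is true of the Mann-Whitney tests only. The second half does not stand, because nothing in the text ranks the two analyses.

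Three other strong readings also fail.
- A reader might quote 40% as the false-positive risk. That needs ten independent tests, and four of them fall at the baseline visits, where a difference cannot be taken for a treatment effect.
- A reader might infer that the plan forgoes the full 14 or 27 points of power. The planned mixed model recovers some of this if it includes baseline.
- A reader might infer that baseline imbalance inflates type I error. Randomization protects the unconditional rate. The cost is lost precision, and error conditional on an imbalance actually seen.

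It can also be said that a single-visit LI difference would not meet the plan's own notion of adaptive reorganization, which Specific Aims ties to correlation with improved outcomes and which separate change-score correlations address. That is fair: the documents do not say an isolated difference would be reported as reorganization. They also give no rule for what such a difference would mean.

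The FDR sentence is no answer, since it covers r-squared and coherence.

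**Conclusion.** The point holds as a low-severity gap in the analysis wording. Followed as written, Aim 2 produces several uncorrected between-arm LI tests that do not measure the stated target, beside a model that may measure it, with no rule on which decides.

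The chance of at least one spurious Mann-Whitney result is about 16% to 23% over the post-baseline visits (26.5% if independent), and 19% to 33% over all five (40% is the independence ceiling). Power at one visit is about 65% by Mann-Whitney, against 67% and 87% for a single-baseline change contrast and 79% and 92% with baseline adjustment, at rho 0.5 and 0.7.

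All these figures rest on the assumed alpha, correlations, modality independence, EEG visit schedule and, for power, the 0.4 SD difference. Taking 72 per arm is optimistic for fMRI. Because ARAT is the primary outcome and Aim 2 is mechanistic, the trial's main conclusion is not at risk.

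**What to change.** Amend the Specific Aim 2 analysis text as follows.

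1. For each modality, make the deciding analysis one between-arm contrast in LI at a visit the sponsor names in advance, adjusted for the averaged baseline LI. Take it from the mixed model, with baseline as a covariate or with baseline means constrained equal across arms. If LI is clearly non-normal, use a rank-based covariance analysis.
2. State the Time levels and the baseline definition for LI, and the visits at which EEG LI is derived.
3. State a simple multiplicity rule across fMRI and EEG, for example Holm. Without one, two tests at 0.05 leave up to 10%.
4. Drop the baseline between-arm tests, and show LI at the other visits descriptively without p-values.

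A lighter alternative is to name Group x Time as the deciding analysis and label the Mann-Whitney tests descriptive. That also settles which result decides, but it still needs items 2 and 3.

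The cost is a wording change before LI data are analysed by arm. It needs no new data and leaves fewer tests.

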
[figure not shown]
Specific Aims

- Aim 1: To investigate the efficacy of active FES vs. passive FES, as measured by changes in behavioral measures. Hypothesis: We hypothesize that improvements in motor function will be significantly greater using the active FES therapy than the passive FES therapy.
- Aim 2: To investigate the relationship between brain functional activation patterns and behavior changes induced by active vs. passive FES intervention. Hypothesis: We hypothesize that changes induced by active FES (as measured by brain fMRI and EEG measures) will show greater adaptive brain reorganization changes (i.e. brain changes that correlate with improved outcomes) than that induced by the passive FES.
- Aim 3: To investigate the relationship between brain white matter integrity and behavior changes induced by active vs. passive FES intervention. Hypothesis: We hypothesize that changes induced by active FES (as measured by brain DTI measures) will show greater adaptive brain reorganization changes (i.e. brain changes that correlate with improved outcomes) than that induced by the passive FES.

Research Design and Methods

This is a prospective, longitudinal study in which stroke patients with upper-limb hemiparesis will be adaptively randomized to two groups: **Active FES (aka the experimental group)**, and **Passive FES aka (the control group)**. Adaptive randomization in our study will be done based on age and severity of UE impairment (see Figure 1).

Participants: 144 patients will be enrolled in the study following inclusion/exclusion criteria below:

Inclusion criteria: ages 50-85 years; new-onset ischemic stroke 12 months prior – chronic time frame; right hand dominant – affected arm; mild to moderate unilateral upper extremity(UE) impairment (Action Research Arm Test; ARAT score > 35) or severe unilateral upper extremity(UE) impairment (ARAT score <= 35); no upper extremity injury or conditions that limited use prior to the stroke; pre-stroke independence with a Modified Rankin Score of 0 or 1, and the ability to provide informed consent on their own behalf.

Exclusion criteria: Inability to competently participate in study procedures, Concurrent upper extremity therapy, other neurological (e.g., AD) or psychiatric disorders.

Note, participants with contraindications to MRI will continue to be eligible for this research and will be asked to participate in both the computer training and the behavioral assessments.

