Randomization: Patients will be adaptively randomized, based on age (50-64 years and 65-85 years), and severity (severe – ARAT > 35, non-severe – ARAT <= 35), to two groups – the active FES group receiving intervention with the active FES (n = 72) and the passive FES group receiving FES only intervention (n=72). Advancing age has a major negative impact on stroke morbidity, mortality; older adults (> 65 years) have increased chance of dying after stroke and being discharged to the skilled nursing facility if they survive, therefore age 65 will be used as a cut-off. There is some evidence that patients with ARAT scores above or below 35 show clear differences in recovery [41], therefore ARAT of 35 will be used as a cutoff.

Subject identification and Recruitment

Subject Identification:

- a) Through referrals by the Stroke Neurology team or other UWHC or UW Rehab hospital or The American Center (TAC) clinicians involved in patient care, in the in-patient or outpatient setting.
- b) Clinicians involved in the care of patients may send recruitment letters to eligible patients and ascertain their interest in study participation.
- c) A stroke service patient log maintained by the UW-Madison Stroke Neurology section UWHC or UW Rehab hospital or TAC clinicians will be used to identify patients.
- d) By posting recruitment flyers in community newsletter, at different locations such as the UWHC, the School of Medicine, UW libraries, the University Station Clinic, St. Mary's hospital, Meriter hospital, as well as UW out-patient clinics and rehab centers outside the Madison area, Madison public libraries, stroke support and other aging support group locations, and on the Principal Investigator, [name] lab

webpage <http://radiology.wisc.edu/research/>. We will also release ads regarding recruitment in the media – in major newspapers such as the Wisconsin State Journal, the Milwaukee Sentinel, in the Isthmus, and through the Wisconsin Public Radio (WPR).

e) [name], the radiologist involved in clinical imaging protocols of patients, will identify patients who are suitable for study participation as they present to the UWHC, UWMF, WIMR, or Health Emotions Research Institute (HERI) for clinical imaging.

f) We have permission to contact participants who have participated in other stroke research conducted by our group ([name] 2013-1561, 2015-0469 and 2018-0398). We propose to contact these patients and ascertain interest in participating in this study.

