be used for correlation analyses between DTI and motor outcome measurements. To test whether change in FA and other diffusion values across multiple time-points correlate with change in scores on the ARAT and the SIS: The difference in each measure, example from time-point 1(T1) to T2 (i.e. change score, Δ FA or other diffusion metrics) will be calculated and separate linear regression analyses performed to see if change in diffusion values significantly correlate with change in behavioral scores. Volume of lesion affecting the white matter will be entered as covariate in the regression analysis.

Sample size considerations: Our sample size analysis is based on the primary outcome measure ARAT. For observing a minimally clinically significant difference on the ARAT of 6 points with a standard deviation of 12, from pre to post intervention, we would need a sample size of 44 participants per cell (Age By Severity with 2 levels each). This would give us 90% power to detect a significant difference. This leads to an estimated sample size of $44 \times 4 = 176$. With 10% additional recruitment to account for data loss due to participant drop-out or poor quality, we propose to recruit a total of $N = 192$ participants in this study.

Given the challenges in recruiting this population (based on our ongoing study – approved under 2010-0004, 2015-0469), we propose to also recruit patients who have contraindications for MRI and allow these patients to complete the behavioral assessments and intervention components of the study.

With the aim of meeting our sample size requirements, and also to recruit a diverse population, we had teamed up with collaborators at Milwaukee, who are also involved in stroke rehab work. Unfortunately, the original PI at Milwaukee has since moved; we have therefore decided to try and meet our goal of 144 at UW Madison and increase our efforts to recruit from the neighboring counties.

Potential Risks and Benefits

EEG Recording: The EEG electrodes are passive and only record ongoing physiological activity. Risks related to the EEG recording system include skin irritation, an unpleasant electrode gel smell, and mild discomfort associated with applying, wearing, and removing electrodes on the scalp, face, chest, and hand.

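### The Aim 2 and Aim 3 tests linking brain change to behaviour change leave out baseline motor severity, which can produce or distort the association the protocol reads as adaptive reorganization

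*Combined protocol and SAP*

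**What the plan says.** In Data Processing/Data Analysis, Aim 2 takes change scores in fMRI- and EEG-derived LI and in behaviour, and "separate correlation (Pearson or Spearman rho) analyses will be performed to see if change in fMRI and EEG significantly correlate" with the behavioural change. No covariate is named, and the text does not say whether the arms are pooled.

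Aim 3 starts with plain Pearson or Spearman correlations between DTI and motor outcomes, then has "separate linear regression analyses performed to see if change in diffusion values significantly correlate with change in behavioral scores". One covariate is given: "Volume of lesion affecting the white matter will be entered as covariate in the regression analysis".

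Severity enters the design instead. Research Design and Methods says: "Adaptive randomization in our study will be done based on age and severity of UE impairment". The Randomization paragraph gives the reason: "There is some evidence that patients with ARAT scores above or below 35 show clear differences in recovery". Both severity groups are enrolled.

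Specific Aims defines what counts as evidence. The hypotheses of Aims 2 and 3 predict that active FES will show "greater adaptive brain reorganization changes (i.e. brain changes that correlate with improved outcomes") than passive FES.

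**The concern.** Randomization protects a comparison of arms. It does not protect a correlation between two changes measured in the same patients. If baseline severity influences both the change in LI or FA and the change in ARAT, the two changes correlate even when patients of equal severity show no link. If the two influences have opposite signs, a real link can be masked.

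The documents support the behavioural half of this path in two ways. The protocol cites some evidence that recovery differs by ARAT. ARAT change also depends on baseline by construction, because the scale stops at 57. The other half, severity to brain change, is plausible but not documented.

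This matters because the protocol identifies adaptive reorganization by its correlation with improved outcome. An artefact in the correlation is therefore an artefact in the evidence.

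**Working it through.** **The plan's own figure.** The only sample-size calculation is for ARAT: 6 points, SD 12, 90% power, 44 per cell. With d = 6/12 = 0.5, a paired t-test at two-sided 5% (assumed, since alpha is not stated) has power 0.900 at n = 44, so the figure reproduces. It has no bearing on Aims 2 and 3, for which no sample size is given.

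**The ceiling.** A patient with baseline ARAT 52 can gain at most 57 − 52 = 5 points. Anyone at 52 or above therefore cannot reach the 6 points that the plan treats as the minimally clinically significant difference.

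**Inputs for the size.** The documents give neither the correlation of severity with either change nor the number with usable imaging (MRI is optional). Assume n = 100, no direct link, and severity correlating a with brain change and b with behaviour change.

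**Formula.** The spurious correlation is r = a × b. By Fisher's z, with m = atanh(r) × √(n − 3), the two-sided 5% test rejects with probability Φ(m − 1.96) + Φ(−m − 1.96).

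Example, a = b = 0.4: r = 0.16; atanh(0.16) = 0.1614; m = 0.1614 × √97 = 0.1614 × 9.849 = 1.590; rejection = Φ(−0.370) + Φ(−3.550) ≈ 0.356.

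The same formula gives the third column below. The other columns come from simulation (20,000 replicates per setting) at one full arm (72) and at both arms pooled (144).

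| a = b | spurious r | unadjusted, n = 100 | unadjusted, n = 72 | unadjusted, n = 144 | severity in model, n = 72 / 144 |
|---|---|---|---|---|---|
| 0.2 | 0.04 | 7% | 6.5% | 7.7% | 5.2% / 5.1% |
| 0.3 | 0.09 | 14% | 11.5% | 19.0% | 4.8% / 5.3% |
| 0.4 | 0.16 | 36% | 26.6% | 48.5% | 5.1% / 5.0% |
| 0.5 | 0.25 | 71% | 57.1% | 85.9% | 5.1% / 5.1% |

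The two correlations need not be equal. With 0.4 for behaviour and 0.1 for brain change, r = 0.4 × 0.1 = 0.04, which is the first row: about 7% at n = 100.

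**The Aim 3 regression.** Let lesion volume correlate l with severity and relate to the two changes only through it. The correlation left after adjusting for lesion volume is (a² − a²l²)/(1 − a²l²). With a = 0.4:

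- l = 0.3: (0.16 − 0.0144)/(1 − 0.0144) = 0.148
- l = 0.5: (0.16 − 0.04)/(1 − 0.04) = 0.125
- l = 0.7: (0.16 − 0.0784)/(1 − 0.0784) = 0.089

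Simulated rejection at n = 144 is 42%, 32% and 18% respectively, against 48.5% with no covariate. Lesion volume helps, but it replaces severity only if it tracks it closely.

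**The case against.** **The hypotheses are comparative.** A reader might infer that a severity artefact would itself confirm Aims 2 and 3. The documents do not support that. Both hypotheses say active exceeds passive, and severity is a randomization factor, so an artefact due to severity alone is expected at similar size in both arms. Aim 2 also compares LI between groups (Mann-Whitney tests, Group × Time mixed model), and this point leaves those analyses untouched. The objection stands: the problem is with the association, not with the contrast between arms.

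**The size is assumed.** This also stands. The Randomization paragraph speaks only of some evidence, and only about recovery. With weak correlations the inflation is small.

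**Lesion volume.** A reader might see its absence from Aim 2 as an inconsistency with Aim 3. It is not one. The covariate is specific to white matter and suits a diffusion outcome. Aim 2 also uses EEG, which the Intervention section describes as recorded during training, and patients who cannot have MRI still take part. Requiring lesion volume in the EEG models would drop them. In Aim 3 the covariate gives partial protection, so the unadjusted rates do not apply to that regression.

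**Over-adjustment and secondary status.** Baseline severity precedes randomization, so it cannot mediate an effect of the intervention. The analyses are secondary to ARAT, but they carry two of the three aims and are to be judged by significance.

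**Conclusion.** The point holds as a possible bias of unknown size. The Aim 2 correlations and the plain Aim 3 correlations are fully exposed; the Aim 3 regression is partly protected by lesion volume. With no direct link and severity correlating 0.2 to 0.5 with both changes, the nominal 5% test rejects about 7% to 71% of the time at an assumed n of 100, and about 5% with severity in the model. These rates rest on normal variables, equal correlations and severity measured without error. They are not estimates of this trial's error rate.

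The documents do not show that an artefact will occur, nor that it would favour active FES. A separate gap remains: no test is specified of whether the brain-behaviour association is stronger under active than passive FES, although the hypotheses call for it.

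**What to change.** In both aims, at each planned time-point, regress the behaviour score on brain change with these covariates:

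- continuous baseline ARAT, and the baseline of the analysed outcome where that is not ARAT, each as the mean of the two baselines as Aim 1 already defines;
- baseline LI or FA;
- age stratum;
- Group, because the trial's own hypotheses make arm a common cause of both changes;
- Group × brain change, which tests the stated hypothesis of a greater association under active FES.

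Keep lesion volume in Aim 3 and add it to the Aim 2 fMRI models. Do not require it in the EEG models, so that patients without MRI are retained. Keep the unadjusted correlations as descriptive.

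Use continuous ARAT rather than the severity stratum. The inclusion criteria describe "severe unilateral upper extremity(UE) impairment (ARAT score <= 35"), while the Randomization paragraph attaches the label severe to scores above 35. Those passages must be reconciled in any case.

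The cost is SAP wording and a few degrees of freedom. Beyond the brain-change term there are five coefficients for an EEG model with ARAT as outcome (baseline ARAT, baseline LI, age, Group, interaction). There are seven for an MRI model with SIS (those five with the relevant brain baseline, plus baseline SIS and lesion volume). Baseline ARAT is already collected for every patient. The interaction will be estimated less precisely than a common slope, and the trial was not sized for it, so report its confidence interval.

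### The Aim 2 and Aim 3 brain-behaviour tests form an open family with no deciding pair or interval and no multiplicity control, so a chance correlation can be reported as adaptive reorganization

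*Combined protocol and SAP*

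**What the plan says.** The hypotheses under Specific Aims say that active FES will show "greater adaptive brain reorganization changes (i.e. brain changes that correlate with improved outcomes" than passive FES. What makes a brain change adaptive is therefore its correlation with outcome.

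The tests are set out under Data Processing/Data Analysis.

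- **Aim 2.** The purpose is given as "To test if change in fMRI and EEG derived LI, across multiple time-points correlate with change in behavioral measures". The method is that "separate correlation (Pearson or Spearman rho) analyses will be performed to see if change in fMRI and EEG significantly correlate with change in behavioral scores". The behavioural list starts with ARAT and ends openly, with "Δ SIS-hand function etc". The interval appears only as an illustration: "The difference in each measure, example from time-point 1(T1) to T2".
- **Aim 3.** The purpose is given as "To test whether change in FA and other diffusion values across multiple time-points correlate with change in scores on the ARAT and the SIS". The method is "separate linear regression analyses performed to see if change in diffusion values significantly correlate with change in behavioral scores", with white-matter lesion volume as a covariate. The other diffusion values are not listed.
- **Multiplicity.** The EEG Data Statistical Analysis paragraph plans Monte-Carlo permutation tests "followed by correction for multiple comparison using false discovery rate (FDR". That paragraph concerns signed r-squared values and coherence estimates. It does not mention the laterality index (LI), the diffusion measures or the behavioural change scores.
- **Lead outcome.** ARAT is called primary only under Sample size considerations.

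**The concern.** Both aims are Specific Aims with directional hypotheses, and in both the planned question is whether changes correlate significantly. Each test crosses a brain measure, a behaviour and an interval, and more than one choice is open on each. Nothing says which cell of that grid answers the question, what happens if cells disagree, or how the error rate over the grid is held down.

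If brain change and recovery were unrelated, following the plan as written would still give an appreciable chance of one significant cell. On the plan's own definition, that cell would mark the brain change as adaptive. At stake is the credibility of the mechanistic conclusions.

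**Working it through.** **1. The significance level.** No alpha or sidedness is stated, so it has to be inferred. The only figure in the plan that allows this is the 44 per cell under Sample size considerations (difference 6, SD 12, 90% power). With d = 6/12 = 0.5, a paired t-test at two-sided 0.05 needs n = 43.995, so 44, with power 90.0% at 44. A one-sided t-test would need 36, and the normal approximation gives (12 × (1.960 + 1.282)/6)² ≈ 42.0, so 43. Two-sided 5% reproduces the figure exactly and is assumed below. This sample size concerns ARAT change; it was not calculated for the correlations.

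**2. The number of tests.** The plan does not fix it. A small reading:

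- Aim 2 brain measures: fMRI LI and EEG LI = 2.
- Aim 2 behaviours: ARAT and SIS-hand function = 2 (the list is open).
- Intervals: mid, post and 1 month, each against the averaged baseline = 3. This is borrowed from the Aim 1 time factor and is an assumption for Aims 2 and 3.
- Aim 2: 2 × 2 × 3 = 12 tests, or 2 × 2 × 1 = 4 with one interval.
- Aim 3 with FA only: 1 × 2 × 3 = 6 tests. With four diffusion metrics (an assumed count): 4 × 2 × 3 = 24.

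**3. Upper guide, independent tests.** The chance of at least one false positive is 1 − 0.95^k:

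- k = 4: 18.5%
- k = 6: 26.5%
- k = 12: 46.0%
- k = 24: 70.8%

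**4. Allowing for correlation.** The tests share measures and a baseline, so they are not independent. Null trials were simulated with brain change independent of behaviour change, a common correlation among measures and among intervals, and Pearson tests at two-sided 5%. Sample size made little difference.

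| Family | Correlation 0.2 | 0.5 | 0.8 |
|---|---|---|---|
| Aim 2, 12 tests | 45% | 41% | 25% |
| Aim 2, one interval, 4 tests | 18% | 17% | 12% |
| Aim 3, FA only, 6 tests | 26% | 25% | 17% |
| Aim 3, four metrics (assumed), 24 tests | 69% | 60% | 35% |

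Repeat simulations agreed to within one or two percentage points, which gives the rounded ranges of 25-45%, 12-18% and 16-27% for the first three rows. Even the smallest entry, 12%, is more than twice 5%.

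**5. Effect of the remedy.** One nominated test per aim at 5% has a 5% error rate for that aim. Benjamini-Hochberg FDR over the 12-, 4- or 6-test family brings the chance of any false positive under the full null to about 4-5%.

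**The case against.** **The aims do not rest on one correlation.** The hypotheses are comparative: more adaptive change under active than passive FES. For Aim 2 the plan also has a linear mixed model of LI with a Group by Time interaction. A reader might infer that a single chance correlation would decide the aim. The documents do not support that for Aim 2, where it would mislabel a change as adaptive but not settle the between-arm question. The reply is weaker for Aim 3, where no between-arm DTI test is stated.

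**The family size is assumed.** This stands. Only one interval is illustrated, and the three used here come from Aim 1. A reader might infer that a false link is more likely than not. The small families give less than 50%; higher figures need counts that the documents do not give, such as four diffusion metrics.

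**The plan already has FDR, and ARAT is primary.** It would be wrong to say that the plan has no multiplicity control, but the FDR step does not reach these tests. ARAT's status, given in the sample-size text, suggests which behaviour should lead. It fixes neither the brain measure nor the interval.

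**The behavioural list is not equally open in both aims.** This also stands. The open-ended list is in Aim 2 only. Aim 3 names ARAT and SIS, and stays open on diffusion metric, SIS domain and interval.

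**Such analyses are usually read as exploratory.** Perhaps, but the plan does not say so here, although it does call analysis 1b post hoc.

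**Leaving Pearson or Spearman open is minor.** Agreed. Taking the smaller of the two p-values raises a single test from 5% to about 7%, and Aim 3 says the choice is made as appropriate. Requiring one coefficient would be a preference.

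**Conclusion.** The concern holds for the brain-behaviour analyses of Aims 2 and 3. These are separate significance tests over several measures and intervals, with no deciding test, no exploratory label and no correction that applies to them. The chance of at least one false significant link is about 25-45% for Aim 2 with 12 tests (12-18% with one interval) and about 16-27% for Aim 3 with FA only, rising with further diffusion metrics. These figures assume two-sided 5% per test, three changes from baseline, and correlations of about 0.2 to 0.8 among measures and among intervals.

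A reader might extend this to the trial's efficacy result. The documents do not support that: the Aim 1 comparison is a separate analysis, and this point leaves it untouched. The plan should be changed, but the fault is confined to the mechanistic claims.

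**What to change.** In the For Specific Aim 2 and For Specific Aim 3 text:

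1. Name one deciding brain-behaviour test per aim, using the primary outcome ARAT with one pre-named brain measure and one interval. Examples are change in fMRI LI (Aim 2) and change in FA in one named tract (Aim 3), each against change in ARAT from averaged baseline to post. The choice of measure and tract is the investigators'.
2. State the significance level and sidedness.
3. Apply the FDR procedure already in the plan to all remaining pairs and intervals within each aim, and label those analyses exploratory.

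This takes a few sentences and one analysis step that the team already intends to use elsewhere, with no new data or participants. The downside is that some exploratory correlations will no longer be called significant.
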